### **10.5. Ethical Conduct of the Study**

The study will be conducted in accordance with legal and regulatory requirements, as well as with scientific purpose, value and rigor and follow generally accepted research practices described in Guidelines for Good Pharmacoepidemiology Practices (GPP) issued by the International Society for Pharmacoepidemiology (ISPE), Good Epidemiological Practice (GEP) guidelines issued by the International Epidemiological Association (IEA), and the Karolinska Institutet's guidelines on Research Conduct.

Per Pfizer's subscription to the ARTIS database, analyses will be conducted by ARTIS researchers and in accordance with ARTIS scientific review policies. The database does not contain any patient identification information (eg, name), except for a unique number assigned for the purpose of linking files.

### **11. MANAGEMENT AND REPORTING OF ADVERSE EVENTS/ADVERSE REACTIONS**

This study involves data that exist as structured data by the time of study start or a combination of existing structured data and unstructured data, which will be converted to structured form during the implementation of the protocol solely by a computer using automated/algorithmic methods, such as natural language processing.

In these data sources, individual patient data are not retrieved or validated, and it is not possible to link (ie, identify a potential association between) a particular product and medical event for any individual. Thus, *the* minimum criteria for reporting an AE (ie, identifiable patient, identifiable reporter, a suspect product, and event) cannot be met.

### **12. PLANS FOR DISSEMINATING AND COMMUNICATING STUDY RESULTS**

Interim reports summarizing the patient characteristics and crude event rates will be submitted to EMA to reflect 2, 4, and 6, years of the study period. Analysis using linked register data through 7 years of follow up will be the basis for a final report to be submitted to EMA. The final report will be included in risk management plan (RMP) updates. Data may be used in regulatory communications external to Sweden for contextualization purposes. Manuscripts based on specific endpoints of interest may be developed for external publication purposes.

### **COMMUNICATION OF ISSUES**

In the event of any prohibition or restriction imposed (eg, clinical hold) by an applicable Competent Authority in any area of the world, or if the party responsible for collecting data from the participant is aware of any new information which might influence the evaluation of the benefits and risks of a Pfizer product, Pfizer should be informed immediately.

#### ANNEX 1. LIST OF STAND ALONE DOCUMENTS

None.

## ANNEX 2. ENCEPP CHECKLIST FOR STUDY PROTOCOLS

**Study title:** An Active Surveillance, Post-Authorization Safety Study (PASS) of Serious Infection, Malignancy, Cardiovascular (CV) and Other Safety Events of Interest among Patients Treated with Tofacitinib for Moderately to Severely Active Rheumatoid Arthritis (RA) within the Swedish, Population-based, Anti-Rheumatic Treatment in Sweden (ARTIS) register

**EU PAS Register® number: EUPAS31157**  
**Study reference number (if applicable): A3921314**

Section 1: Milestones	Yes	No	N/A	Section Number
1.1 Does the protocol specify timelines for				
1.1.1 Start of data collection 				6
1.1.2 End of data collection 				6
1.1.3 Progress report(s)				
1.1.4 Interim report(s)				6
1.1.5 Registration in the EU PAS Register®				6
1.1.6 Final report of study results.				6

Comments:

Section 2: Research question	Yes	No	N/A	Section Number
2.1 Does the formulation of the research question and objectives clearly explain:				8
2.1.1 Why the study is conducted? (e.g. to address an important public health concern, a risk identified in the risk management plan, an emerging safety issue)				8
2.1.2 The objective(s) of the study?				8
2.1.3 The target population? (i.e. population or subgroup to whom the study results are intended to be generalised)				8
2.1.4 Which hypothesis(-es) is (are) to be tested?				8
2.1.5 If applicable, that there is no a priori hypothesis?				8

 Date from which information on the first study is first recorded in the study dataset or, in the case of secondary use of data, the date from which data extraction starts.

 Date from which the analytical dataset is completely available.

Comments:

--

Section 3: Study design	Yes	No	N/A	Section Number
3.1 Is the study design described? (e.g. cohort, case-control, cross-sectional, other design)				9.1
3.2 Does the protocol specify whether the study is based on primary, secondary or combined data collection?				9.2
3.3 Does the protocol specify measures of occurrence? (e.g., rate, risk, prevalence)				9.2
3.4 Does the protocol specify measure(s) of association? (e.g. risk, odds ratio, excess risk, rate ratio, hazard ratio, risk/rate difference, number needed to harm (NNH))				
3.5 Does the protocol describe the approach for the collection and reporting of adverse events/adverse reactions? (e.g. adverse events that will not be collected in case of primary data collection)				

Comments:

No measure of association will be determined in this descriptive study.
 
This is a secondary database study using structured data, no reporting of adverse events is required for this protocol.

---

Section 4: Source and study populations	Yes	No	N/A	Section Number
4.1 Is the source population described?				9.2
4.2 Is the planned study population defined in terms of:				
4.2.1 Study time period				9.2.1
4.2.2 Age and sex				9.2.1
4.2.3 Country of origin				9.2.1
4.2.4 Disease/indication				9.2.1
4.2.5 Duration of follow-up				9.3.2
4.3 Does the protocol define how the study population will be sampled from the source population? (e.g. event or inclusion/exclusion criteria)				9.2.1/9.2.2

Comments:

--

090177e199570500\Approved\Approved On: 13-Feb-2022 20:25 (GMT)

Section 5: Exposure definition and measurement	Yes	No	N/A	Section Number
5.1 Does the protocol describe how the study exposure is defined and measured? (e.g. operational details for defining and categorising exposure, measurement of dose and duration of drug exposure)				9.2
5.2 Does the protocol address the validity of the exposure measurement? (e.g. precision, accuracy, use of validation sub-study)				
5.3 Is exposure categorised according to time windows?				
5.4 Is intensity of exposure addressed? (e.g. dose, duration)				
5.5 Is exposure categorised based on biological mechanism of action and taking into account the pharmacokinetics and pharmacodynamics of the drug?				
5.6 Is (are) (an) appropriate comparator(s) identified?				9.2

Comments:

Exposure is assumed after index until report of discontinuation during risk window for interim reports. Final study SAP will describe methods for accounting for exposure.

Section 6: Outcome definition and measurement	Yes	No	N/A	Section Number
6.1 Does the protocol specify the primary and secondary (if applicable) outcome(s) to be investigated?				9.3.3
6.2 Does the protocol describe how the outcomes are defined and measured?				9.7.2
6.3 Does the protocol address the validity of outcome measurement? (e.g. precision, accuracy, sensitivity, specificity, positive predictive value, use of validation sub-study)				9.7.2
6.4 Does the protocol describe specific outcomes relevant for Health Technology Assessment? (e.g. HRQoL, QALYs, DALYS, health care services utilisation, burden of disease or treatment, compliance, disease management)				

Comments:

Section 7: Bias	Yes	No	N/A	Section Number
7.1 Does the protocol address ways to measure confounding? (e.g. confounding by indication)				9.7.2
7.2 Does the protocol address selection bias? (e.g. healthy user/adherer bias)				9.7.2
7.3 Does the protocol address information bias? (e.g. misclassification of exposure and outcomes, time-related bias)				9.7.2

Comments:

Interim reports are crude analyses, final study analyses will be determined by SAP.

Section 8: Effect measure modification	Yes	No	N/A	Section Number
8.1 Does the protocol address effect modifiers? (e.g. collection of data on known effect modifiers, subgroup analyses, anticipated direction of effect)				

Comments:

Section 9: Data sources	Yes	No	N/A	Section Number
9.1 Does the protocol describe the data source(s) used in the study for the ascertainment of:				
9.1.1 Exposure? (e.g. pharmacy dispensing, general practice prescribing, claims data, self-report, face-to-face interview)				9.4
9.1.2 Outcomes? (e.g. clinical records, laboratory markers or values, claims data, self-report, patient interview including scales and questionnaires, vital statistics)				9.4
9.1.3 Covariates and other characteristics?				9.4
9.2 Does the protocol describe the information available from the data source(s) on:				
9.2.1 Exposure? (e.g. date of dispensing, drug quantity, dose, number of days of supply prescription, daily dosage, prescriber)				
9.2.2 Outcomes? (e.g. date of occurrence, multiple event, severity measures related to event)				9.4
9.2.3 Covariates and other characteristics? (e.g. age, sex, clinical and drug use history, co-morbidity, co-medications, lifestyle)				9.4
9.3 Is a coding system described for:				
9.3.1 Exposure? (e.g. WHO Drug Dictionary, Anatomical Therapeutic Chemical (ATC) Classification System)				

090177e199570500\Approved\Approved On: 13-Feb-2022 20:25 (GMT)

Section 9: Data sources	Yes	No	N/A	Section Number
9.3.2 Outcomes? (e.g. International Classification of Diseases (ICD), Medical Dictionary for Regulatory Activities (MedDRA))				9.4,9.7.2
9.3.3 Covariates and other characteristics?				
9.4 Is a linkage method between data sources described? (e.g. based on a unique identifier or other)				9.4,9.7.2

Comments:

--

Section 10: Analysis plan	Yes	No	N/A	Section Number
10.1 Are the statistical methods and the reason for their choice described?				9.7
10.2 Is study size and/or statistical precision estimated?				
10.3 Are descriptive analyses included?				9.7
10.4 Are stratified analyses included?				9.7
10.5 Does the plan describe methods for analytic control of confounding?				
10.6 Does the plan describe methods for analytic control of outcome misclassification?				
10.7 Does the plan describe methods for handling missing data?				
10.8 Are relevant sensitivity analyses described?				9.2.4

Comments:

This is a descriptive study. SAP to govern final adjusted analyses pending feasibility.
---

Section 11: Data management and quality control	Yes	No	N/A	Section Number
11.1 Does the protocol provide information on data storage? (e.g. software and IT environment, database maintenance and anti-fraud protection, archiving)				9.6
11.2 Are methods of quality assurance described?				9.8
11.3 Is there a system in place for independent review of study results?				9.8

Comments:

--

090177e199570500\Approved\Approved On: 13-Feb-2022 20:25 (GMT)

Section 12: Limitations	Yes	No	N/A	Section Number
12.1 Does the protocol discuss the impact on the study results of:				
12.1.1 Selection bias?				9.9
12.1.2 Information bias?				9.9
12.1.3 Residual/unmeasured confounding? (e.g. anticipated direction and magnitude of such biases, validation sub-study, use of validation and external data, analytical methods).				9.9
12.2 Does the protocol discuss study feasibility? (e.g. study size, anticipated exposure uptake, duration of follow-up in a cohort study, patient recruitment, precision of the estimates)				8. 9.3.3, 9.5. 9.7.2

Comments:

--

Section 13: Ethical/data protection issues	Yes	No	N/A	Section Number
13.1 Have requirements of Ethics Committee/ Institutional Review Board been described?				10.4
13.2 Has any outcome of an ethical review procedure been addressed?				
13.3 Have data protection requirements been described?				

Comments:

--

## Appendix 1. TABLE SHELLS FOR SAFETY REPORTS

### The Template Of Semiannual Reports

XXXX Data report  
DD Month YYYY

Table no.	Description	Comment
1	Demographics	Demographic data not included in Table 3a
1b	Person-years of follow-up and treatment	By sex and treatment indication.
3a-3b	Manchester template	Table 3a describing the surveillance cohort. Table 3b with characteristics at first treatment start with the present biologic drug, all patients registered, and patients with Rheumatoid Arthritis (RA) or Polyarthritis (PA).

---

090177e199570500\Approved\Approved On: 13-Feb-2022 20:25 (GMT)

**Table 1. Number Of Patients Ever Treated, And Currently On Drug, By Treatment Indication**

	Treatment indication a							Missing
	Overall	RA	JA	PA	PsA	AS	OT	
Patients ever on drug – n (%)								
Male								
Female								
All								
Patients currently on drug b – n (%)								
Male								
Female								
All								

a. RA=rheumatoid arthritis, JA=juvenile arthritis, PA=polyarthritis, PsA=psoriatic arthritis, AS=ankylosing spondylitis, OT=other rheumatic disease.  
b. It is acknowledged that data at time of data lock may be incomplete, and thus information on exposure may lag.

**Table 1b. Number of Person-years of Follow-up and of Time on Biologic Treatment; by Sex and Treatment Indication**

Person-years of follow-up	Total	Treatment indication a					OT
		RA	JA	PA	PsA	AS	
Male							
Female							
All							
on treatment							
Male							
Female							
All							

a. RA=rheumatoid arthritis, JA=juvenile arthritis, PA=polyarthritis, PsA=psoriatic arthritis, AS=ankylosing spondylitis, OT=other rheumatic disease

090177e199570500\Approved\Approved On: 13-Feb-2022 20:25 (GMT)

**Table 2. Distribution of Safety Events Of Interest By Seriousness, And Treatment Indication - Cumulatively During The Follow-Up Period**

Report according to a revised version of the template

Period of observation	Cumulatively	From
	This period	From
		To

**Table 3a. Variables Describing The Surveillance Cohort**

Variable	N	%
New treatments		
New treatments in this time period		
Newly recorded treatments before this period		
Previously reported cumulative number of treatments		
Current cumulative number of treatments		
Cumulative number of treatments by gender		
	Males	
	Females	
	Unknown	
Cumulative number of patients by gender		
	Males	
	Females	
	Unknown	
Cumulative Number of patients by Age at registration		

090177e199570500\Approved\Approved On: 13-Feb-2022 20:25 (GMT)

**Table 3a. Variables Describing The Surveillance Cohort**

Variable	N	%
	<18	
	18-34	
	35-44	
	45-54	
	55-64	
	65-74	
	75+	
	Unknown	
Person Years - Time on actual biologic therapy		
	Male	
	Females	
	All	
Person Years - Total follow-up		
	Male	
	Female	
	All	

090177e199570500\Approved\Approved On: 13-Feb-2022 20:25 (GMT)

**Table 3b. Characteristics At First Treatment Start With The Present Biologic Drug, All Patients Registered, And Patients With Rheumatoid Arthritis (RA)**

Variable	Mean	SD
Year since diagnosis		
HAQ among RA		
	Female	
	Male	
	Total	
DAS28 among RA		
	Female	
	Male	
	Total	
PAIN VAS among RA		
	Female	
	Male	
	Total	
Tender joint count among RA or PA patients		
	Female	
	Male	
	Total	
Swollen joint count among RA or PA patients		
	Female	
	Male	

**Table 3b. Characteristics At First Treatment Start With The Present Biologic Drug, All Patients Registered, And Patients With Rheumatoid Arthritis (RA)**

Variable	Mean	SD
	Total	
CRP among all patients		
	Female	
	Male	
	Total	
CRP among RA or PA patients		
	Female	
	Male	
	Total	
ESR among all patients		
	Female	
	Male	
	Total	
ESR among RA or PA patients		
	Female	
	Male	
	Total	
Global Health VAS in all patients		
	Female	
	Male	

**Table 3b. Characteristics At First Treatment Start With The Present Biologic Drug, All Patients Registered, And Patients With Rheumatoid Arthritis (RA)**

Variable	Mean	SD
	Total	
Global Health VAS in RA or PA patients	Female	
	Male	
	Total	
Ever treated with any other biologics	All	
	Males	
	Females	
Previously treated with any other biologics	All	
	Males	
	Females	

---

CRP=c-reactive protein; DAS=disease activity scale ESR=erythrocyte sedimentation rate; HAQ=health assessment questionnaire; PA=polyarthritis; RA=rheumatoid arthritis; SD=standard deviation; VAS=visual analog scale

090177e199570500\Approved\Approved On: 13-Feb-2022 20:25 (GMT)

## Appendix 2. Table Shells For Comparative Safety Reports

These table shells describe the general outline and contents of tables in comparative safety reports based on register-linkage data. Details of outcome definitions will be agreed upon before each report.

Table I. Baseline characteristics of Swedish RA patients initiating tofacitinib 201X-20XX, and comparator cohorts									
Status at entry	Exposed Tofacitinib	Third biologic		Second biologic		Comparator Cohorts First biologic			
		TNFi	Non-TNFi	TNFi	Non-TNFi	TNFi	Non-TNFi	Biologics-naive	General population
N patients									
Demographics									
Age at start of follow-up (median, IQR)									
Gender (% females)									
Smoking (current/previous/never)									
RA-related characteristics									
Rheumatoid factor positive (%)									
Disease duration at start of follow-up (median, IQR)									
Calendar year of start of follow-up (median)									
DAS28 at start of follow-up (median, IQR)									
HAQ at start of follow-up (median, IQR)									
Concomitant DMARDs at start of follow-up (%)									
Oral steroids at start of follow-up (%)									
NSAIDs at start of follow-up (%)									
Number of previous biologics									
0									
1									
2									
3+									
Comorbidity at start of follow-up									
Hx of malignancy (%)									
Hx of hosp infection (%)									
Hx of joint hip/knee replacement (%)									
Hx of COPD (%)									
Hx of diabetes mellitus (%)									
Hx of MI (%)									

090177e199570500\Approved\Approved On: 13-Feb-2022 20:25 (GMT)

Table I. Baseline characteristics of Swedish RA patients initiating tofacitinib 201X-20XX, and comparator cohorts									
Status at entry	Exposed Tofacitinib	Third biologic		Second biologic		Comparator Cohorts First biologic			
		TNFi	Non-TNFi	TNFi	Non-TNFi	TNFi	Non-TNFi	Biologics-naive	General population
Hx of hypertension (%)									
Hx of coronary heart disease (%)									
Hx of stable angina pectoris									
Hx of coronary artery procedures (%)									

090177e199570500\Approved\Approved On: 13-Feb-2022 20:25 (GMT)

Table I. Baseline characteristics of Swedish RA patients initiating tofacitinib 201X-20XX, and comparator cohorts									
Status at entry	Exposed Tofacitinib	Third biologic		Second biologic		Comparator Cohorts First biologic			
		TNFi	Non-TNFi	TNFi	Non-TNFi	TNFi	Non-TNFi	Biologics-naive	General population
Total days spent in hosp (median, IQR)									
Reason for discontinuing previous biologic									
Safety, of those with information (%)									
Inefficacy, of those with information (%)									
Other, of those with information (%)									
Missing, of total (%)									

COPD=Chronic obstructive pulmonary disease; DAS: Disease activity scale; DMARD=disease modifying antirheumatic drug; HAQ= health assessment questionnaire; Hx=history IQR=interquartile range; MI=myocardial infarction; N=count; NSAID = non-steroidal anti-inflammatory drug; RA=Rheumatoid Arthritis; TNFi=tumor necrosis factor inhibitor.

090177e199570500\Approved\Approved On: 13-Feb-2022 20:25 (GMT)

Table II. Total number of events, crude and standardized incidence rates							
Outcome	Cohort	Patients	Events	Person-Years	IR	Std IR	Mean follow-up, yrs
For each event of interest							
	Tofacitinib						
	0 previous biologics						
	1 previous biologics						
	2 previous biologics						
	3+ previous biologics						
	Third bio starters, TNFi						
	Third bio starters, non-TNFi						
	Second bio starters, TNFi						
	Second bio starters, non-TNFi						
	First bio starters, TNFi						
	First bio starters, non-TNFi						
	Bonaïve RA Patients						
	General Population						
Notes: IR, Incidence Rate, RA=rheumatoid arthritis; Std IR standardised incidence rate to the age/sex distribution in the tofacitinib cohort; TNFi=tumor necrosis factor inhibitor; yrs=years.							

090177e199570500\Approved\Approved On: 13-Feb-2022 20:25 (GMT)

090177e199570500\Approved\Approved On: 13-Feb-2022 20:25 (GMT)

Table III. Results from adjusted Cox regressions comparing tofacitinib initiators to comparator cohorts for each outcome									
Outcome	Tofacitinib initiators vs.	HRa	95% CI	HRb	95% CI	HRc	95% CI	HRd	95% CI

Notes: Analysis was only made for comparisons where both cohort had at least 5 observed events. HR: Hazard Ratio. CI: Confidence Interval.  HRa: stratified for year at start, adjusted for age and sex.  HRb: stratified for year at start, adjusted for age, sex, prior number of days in inpatient care, history of infection, cancer, MI, diabetes, COPD, and joint replacement surgery.  HRc: stratified for year at start, adjusted for age, sex, prior number of days in inpatient care, history of infection, cancer, MI, diabetes, COPD, and joint replacement surgery, Rheumatoid factor, HAQ(linear), RA disease duration, DAS28(linear), DMARDs, steroids. Complete case analysis.  HRd: as HRc but using a missing indicator, and quartiles, for HAQ and DAS28.
									

Table IV. Results from crude and adjusted Cox regressions comparing tofacitinib to biologic DMARDs (bDMARDs), stratified by the number of bDMARDs									
Outcome	Number of previous biologics	HRa	95% CI	HRb	95% CI	HRc	95% CI	HRd	95% CI
Each event	0								
	1								
	2								
	Aggregate estimate								

Notes: Analysis was only made for comparisons where both cohorts had at least 5 observed events. HR: Hazard Ratio. CI: Confidence Interval.  HRa: stratified for year at start, adjusted for age and sex.  HRb: stratified for year at start, adjusted for age, sex, prior number of days in inpatient care, history of infection, cancer, MI, diabetes, COPD, and joint replacement surgery.  HRc: stratified for year at start, adjusted for age, sex, prior number of days in inpatient care, history of infection, cancer, MI, diabetes, COPD, and joint replacement surgery, Rheumatoid factor, HAQ(linear), RA disease duration, DAS28(linear), DMARDs, steroids. Complete case analysis.
									

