#### 9.5. Study Size

All eligible patients in the Swedish registers will be included, with no upper limit on the sample size. The feasibility of more refined comparative analyses to evaluate safety concerns that adequately adjust for patient channeling and confounders will be assessed at an interim time point and after 7 years will be based on statistical power. Since the comparator groups will be a magnitude larger than the tofacitinib treated group, statistical power will be limited by the uptake of tofacitinib, which is difficult to estimate a priori. While the primary objective of the protocols is active surveillance, conducting quantitative, confounding controlled comparisons will depend on having a sufficient sample.

Table 2 and Table 3 below describe the power to detect a 2-fold difference in event rates between tofacitinib-initiators and bDMARD-initiators assuming the following:

- $\alpha=0.05$ ;
- 3 different bDMARD-treated patient population sizes (reflecting roughly range of EU registers):  $n=11100$ ,  $n=5050$ ,  $n=1650$ ;
- 4 different tofacitinib-treated patient population sizes:  $n=100$ ,  $n=250$ ,  $n=500$ ,  $n=1000$ ;
- Estimated rates on bDMARD of 30/1000 person years (PY) (eg, serious infection), 10/1000 PY (eg, malignancy excluding NMSC), and 6/1000 PY (eg, major adverse cardiovascular event (MACE)) based on previous analysis with registers (Pfizer, internal data);
- 7-year study period;
- Constant rate of accrual;
- 5% annual loss to follow up among tofacitinib-treated patients.

Additionally, Table 2 assumes a 0% annual rate of switching off tofacitinib, as would be true for a drug with very high persistence or for an analysis following the once exposed always at risk paradigm. Table 3 assumes a 30% annual rate of switching from tofacitinib to a bDMARD over the study period, as previously demonstrated in the EU for bDMARDs in Italy.

For an event with a rate of 30/1000 PY, such as serious infections, 250 patients would allow sufficient power to detect a 2-fold difference in rates between tofacitinib and bDMARD-exposed patients assuming very high persistence (Table 2), while 500 tofacitinib exposed patients would be nearly sufficient if 30% of tofacitinib treated patients switched off of tofacitinib annually.

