bDMARD rate ~10/1000 PY (eg, malignancy)			
100	0.06	0.06	0.06
250	0.16	0.16	0.15
500	0.33	0.32	0.30
1000	0.64	0.60	0.50
bDMARD rate ~ 6/1000 PY (eg, MACE)			
100	0.04	0.04	0.04
250	0.09	0.09	0.09
500	0.19	0.19	0.18
1000	0.40	0.38	0.32

Based on the first 9 months of enrolment of tofacitinib-exposed patients in ARTIS, 344 patients are projected to be enrolled in the first 24 months, allowing at least 5 years follow up by the end of the planned study period, assuming the initial rate remains constant over the period.

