Meta-analytic methods that attempt to combine the results of this study with results from other participating European registers will be used to summarize the findings across studies. A quantitative meta-analysis would permit an estimate of an average effect across the studies with more statistical power than the individual studies, provided a formal evaluation did not reveal substantial heterogeneity. Meta-analysis may reveal between-study heterogeneity such that a subset of more comparable studies could be included in a single estimate. Heterogeneity may be expected, for example due to differences in local prescribing practices, patient populations, competing risks, and prevalence of comorbidities and risk factors. Such heterogeneity would exist even if the coding for endpoint definitions and reporting could be harmonized across registers. In the presence of such heterogeneity, pooling across the registers is not informative as the generalizability of such an estimate is unknown. Pending feasibility of comparative analysis, meta-analytic methods will be determined a priori and described in an approved SAP.

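### Hazard ratios are shown only where both cohorts have at least 5 observed events, which inflates the displayed HRs for comparisons with few expected tofacitinib events

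*Protocol*

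**What the plan says.** Appendix 2 of the protocol gives table shells for the comparative reports. The note under Table III (adjusted Cox regressions by outcome and comparator) reads "Analysis was only made for comparisons where both cohort had at least 5 observed events". The note under Table IV (tofacitinib against bDMARDs by number of previous biologics, with an aggregate row) repeats it: "Analysis was only made for comparisons where both cohorts had at least 5 observed events".

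Section 9.5 describes the imbalance between cohorts: "Since the comparator groups will be a magnitude larger than the tofacitinib treated group, statistical power will be limited by the uptake of tofacitinib". It also gives the enrolment projection, "344 patients are projected to be enrolled in the first 24 months, allowing at least 5 years follow up", and the planning rates, "Estimated rates on bDMARD of 30/1000 person years (PY) (eg, serious infection), 10/1000 PY (eg, malignancy excluding NMSC), and 6/1000 PY".

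Three other places bear on the point:
- Table II of Appendix 2 lists events, person-years and crude and standardised rates for every outcome and cohort, with no event threshold.
- Section 9.7.2 says that whether formal comparisons with bDMARDs are made is settled in advance on power.
- Section 9.7.2 also foresees pooling with other registers: "A quantitative meta-analysis would permit an estimate of an average effect across the studies with more statistical power than the individual studies". The methods are left to the SAP.

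**The concern.** The rule makes the existence of an HR depend on the result. One of the two cohorts in every comparison is tofacitinib. When the other is about ten times larger, the comparator passes the threshold long before tofacitinib does. For a rare outcome, an HR is then printed when tofacitinib happens to have many events and left blank when it has few. Even with no effect, the printed HRs lie above 1 on average.

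This bears on endpoints that matter here. Section 7.2 names lung cancer and lymphoma as important identified risks, and lymphoma is to be split by subtype. A wide interval is only partial protection, because the interval is selected along with the estimate.

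**Working it through.** **Inputs**
- Threshold: 5 observed events in each cohort (notes to Tables III and IV).
- Comparator to tofacitinib person-time: 10 to 1 (from Section 9.5), with 30 to 1 as a sensitivity check.
- Planning rates: 30, 10 and 6 per 1000 person-years (PY) for serious infection, malignancy and MACE (Section 9.5).
- Rarer endpoints: the protocol gives no rate. I assume 0.5 to 2 per 1000 PY.
- True HR: 1. A Poisson rate ratio stands in for the Cox HR.

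**Step 1: person-time.** The simplest reading of Section 9.5 is 344 × 5 = 1,720 PY. With enrolment spread over the first 24 months, follow-up of 5 to 7 years and 5% annual loss, the same 344 patients give about 1,770 PY. If the pace of 172 a year held for 7 years, 172 × 7 = 1,204 patients would give about 3,750 PY with 5% annual loss.

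**Step 2: expected tofacitinib events, overall comparison.**
- Serious infection: 1,720 × 0.030 = 51.6.
- Malignancy: 1,720 × 0.010 = 17.2.
- MACE: 1,720 × 0.006 = 10.3.
- Rare endpoints: from 1,770 × 0.0005 = 0.9 to 3,750 × 0.002 = 7.5.

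**Step 3: Table IV strata.** If patients divide evenly over three strata, malignancy has 17.2/3 = 5.7 expected events per stratum and MACE 10.3/3 = 3.4. For MACE, 1,720 PY ignores both switching and later enrolment. Taking 1,204 patients, 5% loss and the 30% annual switching of Section 9.5 gives about 1,980 PY (before the 90-day extension), so 11.9 events overall and 4.0 per third. The conclusion is the same.

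**Step 4: effect of the rule.** Let X be Poisson with mean μ, the expected tofacitinib count, and let the comparator be large. The HR is shown with probability P(X ≥ 5). Its mean when shown is E[X | X ≥ 5]/μ = P(X ≥ 4)/P(X ≥ 5). For μ = 3 this is 0.353/0.185 = 1.91.

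| Expected events μ | Probability HR is shown | Mean ratio when shown (true value 1) |
|---|---|---|
| 2 | 0.05 | 2.7 |
| 3 | 0.18 | 1.9 |
| 3.4 (MACE, one third) | 0.26 | 1.7 |
| 4 | 0.37 | 1.5 |
| 5 | 0.56 | 1.3 |
| 5.7 (malignancy, one third) | 0.68 | 1.2 |
| 8 | 0.90 | 1.06 |
| 10.3 (MACE overall) | 0.98 | 1.02 |
| 17.2 (malignancy overall) | about 1 | 1.00 |

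Simulating the comparator count as well, at 10 or 30 to 1, gives nearly the same ratios. At 10 to 1, the 95% interval of a shown null HR lies wholly above 1 in about 54% of cases at μ = 2, 18% at μ = 3 and 5.6% at μ = 5. Without a threshold the figure is about 3%.

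**Step 5: dependence on the size ratio.** With equal cohorts the double threshold is symmetric and the typical shown ratio is 1.0. With a comparator half the size of tofacitinib and μ = 5, it falls to about 0.58.

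**The case against.** Four points can be made for the plan.

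First, a minimum event count is an ordinary safeguard for Cox models with as many covariates as these. That is fair as to purpose. But stability can be secured with an expected count or a penalised fit, without selecting on the exposed cohort's outcome.

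Second, a reader might infer that reassuring results vanish from the report. They do not. Table II keeps all counts and rates, and Section 9.1 promises 95% intervals for rates in all four cohorts. What is lost is the adjusted estimate, which only Tables III and IV provide.

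Third, a reader might infer that the Table IV aggregate and the meta-analysis are biased. The documents do not support this. The aggregate is undefined and could come from a stratified model using every event, and the meta-analysis inputs are left to the SAP. The bias carries over only if qualifying HRs alone are combined. In that case, inverse-variance pooling of three equal strata under no effect gives typically 1.22 for malignancy (5.7 each) and 1.72 for MACE (3.4 each). Using all events, the median is about 0.98 to 0.99.

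Fourth, Section 9.7.2 decides formal comparisons beforehand on power, which might keep the sparsest outcomes out. This helps, but it is not said to operate by outcome or stratum, and the table note still selects within whatever is compared.

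Two further overstatements should be avoided. The ratio 5/3 = 1.67 is not a floor for shown HRs at 3 expected events: the comparator count varies too, and more than a quarter of shown null ratios fall below it. Nor does tofacitinib always bind. The shells split bDMARDs into third-biologic TNFi and non-TNFi groups, which may be small, and there the bias can vanish or reverse.

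**Conclusion.** The point holds for comparisons with fewer than about 6 to 8 expected tofacitinib events against a much larger comparator. There the displayed HRs are inflated under no effect, from about 1.3 at 5 expected events to 2.7 at 2. The Table IV part rests on the protocol's own rates plus an assumed even split over strata. The rare-endpoint part rests on assumed rates of 0.5 to 2 per 1000 PY. Overall results for serious infection, all malignancy and MACE are essentially unaffected. Covariate adjustment does not remove a selection made on the event count. Since the full counts remain visible and the HRs are a secondary output subject to feasibility, this is a cheap improvement rather than a flaw that undermines the study.

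**What to change.** Replace the observed-count threshold in both notes with one that does not use the tofacitinib outcome. For example, fit the Cox model where expected tofacitinib events are at least 5, with expected events = tofacitinib person-years × comparator rate standardised to the tofacitinib age and sex distribution. Table II already supplies both quantities.

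Below that level, report the age- and sex-standardised rate ratio with an exact or penalised-likelihood 95% CI for every pre-specified outcome, zero counts included. Use the same fallback if the expected count qualifies but the observed count is too low for the Cox fit, so that no cell is left blank because of the result.

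State that the Table IV aggregate and this study's contribution to any meta-analysis use all strata, whatever the observed count.

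The cost is a few sentences in the table notes and the SAP, slightly more analysis work and a few more wide intervals. No new data are needed. The change should be made before comparative results are seen.
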